2.2 Background information on the investigational product

SH is a glycosaminoglycan with viscoelastic rheology. It is composed of repeating units of N-acetyl-D-glucosamine and sodium-D-glucuronate. [20] It has a high molecular weight (2.5–4 million daltons) and low protein content. Its half-life is 1 day in aqueous humor and 3 days in vitreous humor. [3] SH is naturally found in various tissues of the body, mainly found in high concentrations in vitreous humor, synovial fluid, and umbilical cord.

SH is used in various concentrations in many of the currently available OVDs and can be extracted and purified from different sources, such as rooster combs or by bacterial cell-assisted fermentation. Depending on the extraction source, the molecular weight may vary, but the structure remains the same. The SH used in PRO-149, like that in Healon® EndoCoat, is a highly purified extract obtained by bacterial fermentation, well tolerated by the eye, non-antigenic, and non-pyrogenic.

2.2.1 Efficacy of the investigational product

The efficacy of various SH-containing OVDs has been established in several clinical studies. A multicenter, double-blind, randomized clinical study was conducted with the Healon® EndoCoat OVD, which contains the same concentration of SH as PRO-149, in 400 patients undergoing phacoemulsification and IOL implantation.

Two hundred patients were assigned to the Healon® EndoCoat group and 200 to the control group, corresponding to Viscoat®. Efficacy was measured by CEC protection. Healon® EndoCoat demonstrated non-inferiority when compared to Viscoat® in the CEC count from pre-surgery to 3 months post-surgery ($p < 0.0001$, 1-tailed t-test, $\delta = 5\%$). The mean percentage changes observed were -4.7% for Healon® EndoCoat and -7.0% for Viscoat® with a percentage point difference of 2.3 (90% confidence interval: [0.23, 4.33]). [21]

2.2.2 Safety of the investigational product

In the same clinical study described above, safety was evaluated by the cumulative rate of intraocular pressure (IOP) peaks ≥ 30 mmHg and the presence of adverse events (AEs).

The results demonstrated that the percentage of subjects with IOP spikes in the Healon® EndoCoat group was not higher than that in the Viscoat® group (cumulative percentage of subjects with IOP ≥ 30 mmHg during the study ($p = 0.0003$, $\delta = 0.13$, 90% confidence interval [-1.74, 7.72]).

Surgical complications reported were 3% (6/200) in the Healon® EndoCoat group and 8% (16/200) in the Viscoat® group.

Regarding AEs, 39 subjects reported an AE during the study. None of these were considered unexpected. Ninety-two percent of the AEs were IOP ≥ 30 mmHg; the incidence of this AE was 10.5% in the Healon® EndoCoat group and 7.5% in the Viscoat® group. The three AEs that did not correspond to an increase in IOP included: one subject in the Healon® EndoCoat group who developed cystoid macular edema (requiring treatment) and two subjects in the Viscoat® group: one subject who required IOL exchange for haptic damage and one who underwent removal of an ocular surface foreign body. None of the above AEs were considered related to OVD use. [21]

List of incidents or adverse reactions reported with a 3% sodium hyaluronate viscoelastic or with the use of intraocular sodium hyaluronate: [21] [22]

- Eye inflammation (iritis, hypopyon, endophthalmitis)
- Increased intraocular pressure
- Corneal edema
- Secondary glaucoma
- Corneal decompensation

All of the described incidents or adverse reactions may potentially occur with the use of PRO-149 or Healon® EndoCoat. [21] [22]

2.2.3 Summary of the pharmaceutical development of the investigational product

The development of PRO-149 included physicochemical and rheological characterization tests, as well as stability tests. In addition, preclinical studies were conducted in New Zealand albino rabbits using two models: an aqueous exchange model and an aqueous humor replacement model with subsequent AC washout. [23]

Twenty eyes of 20 research subjects (rabbits) were studied and divided into two groups of 10, group 1 underwent aqueous humor exchange (anterior chamber exchange, via paracentesis, 0.05 mL of aqueous humor for 0.05 mL of OVD) and group 2 underwent AC lavage (exchange of the total volume of aqueous humor in AC for the OVD, which was lavaged and replaced with balanced saline solution by manual I/A). In turn, both groups were subdivided into A and B, with 5 subjects per group, for the PRO-149 and Healon® EndoCoat groups.

The primary safety variables were IOP, corneal opacity, AC cellularity and flare, presence of fibrin, iris congestion, conjunctival hyperemia, discharge, conjunctival edema, and incidence of AEs. Toxicity variables included abnormalities in histopathological examinations of the tissues studied.

In both models, no statistically significant differences were observed in the safety variables between both DVOs. [23]

2.3 Background on the research

2.3.1 From the research question

There is no prior data on PRO-149 in clinical trials. However, the efficacy and tolerability of SH-containing OVDs have been previously tested.

2.4 Risk benefit assessment

2.4.1 Known potential risks

OVDs are safe formulations whose use during phacoemulsification surgery and IOL placement has been recognized as beneficial in increasing the safety of the procedure. Since SH is a polysaccharide naturally present in many body tissues, it is very well tolerated by the human eye. However, transient postoperative inflammation and increased IOP have been reported in clinical studies with these OVDs.

Cataract surgery, currently performed by phacoemulsification, is the most frequently performed surgery worldwide by ophthalmic surgeons [18]. Like any medical procedure, it is not exempt from complications; however, the risk-benefit balance is favorable to the procedure.

2.4.2 Known potential benefits

The benefits are described in three orders. First, for the study subjects, it restores vision lost directly due to lens opacity. Second, for phacoemulsification surgery, the use of an OVD protects structures such as the CECs and facilitates surgical maneuvers. Third, for the investigational product, it documents the safety profile of PRO-149.

2.5 Problem statement

A few decades ago, cataract surgery was performed with the aid of an air bubble to maintain the AC formation. This technique provided poor protection to the structures and was minimally effective in maintaining the AC formation. With the advent of OVDs, this changed, allowing cataract surgery to evolve toward a safer process.

However, there is no ideal OVD; each case or even each surgical step may require specific OVD characteristics. For this reason, various OVDs have been developed, ranging across the spectrum from dispersivity to cohesiveness.

PRO-149 has rheological characteristics that could make it a safe and efficient dispersive OVD.

2.6 Justification

Unlike pharmaceutical compounds, in which the active ingredient maintains its pharmacokinetic and pharmacodynamic properties between formulations, provided the concentrations and compatibility with excipients are respected, OVDs cannot be properly designated as generics.

The chain length, pH, osmolarity, presence of other solutes, polymer conformation, and electrical charge can vary between these apparently identical formulations, which would directly affect their rheological properties and, consequently, their clinical behavior.

This study is necessary to test the safety of PRO-149 by comparing it with the safety found in a product already on the market (Healon® EndoCoat) and to understand its behavior during phacoemulsification surgery.

3. Objectives and hypotheses

3.1 Primary objectives

To evaluate the safety of PRO-149, manufactured by Laboratorios Sophia, S.A. de C.V., when used as an OVD during phacoemulsification surgery and intraocular lens (IOL) placement in patients diagnosed with senile cataracts, compared to Healon® EndoCoat.

3.2 Specific objectives

- To compare the safety of OVD PRO-149 versus Healon® EndoCoat in cataract phacoemulsification surgery and intraocular lens implantation, through changes in pre and postoperative CEC density.
- To compare the safety of OVD PRO-149 versus Healon® EndoCoat in cataract phacoemulsification surgery and intraocular lens implantation, through changes in IOP.

3.3 Secondary objectives

- To compare the safety of OVD PRO-149 versus Healon® EndoCoat in cataract phacoemulsification surgery and intraocular lens implantation, with the incidence of AEs.
- To compare the safety of OVD PRO-149 versus Healon® EndoCoat in cataract phacoemulsification surgery and intraocular lens implantation, through changes in central corneal thickness.
- To compare the safety of OVD PRO-149 versus Healon® EndoCoat in cataract phacoemulsification surgery and intraocular lens implantation, with the presence of cellularity in postoperative AC.
- To compare the safety of OVD PRO-149 versus Healon® EndoCoat in cataract phacoemulsification surgery and intraocular lens implantation, with the presence of postoperative AC flare.
- To compare the best-corrected visual acuity obtained after cataract phacoemulsification surgery and intraocular lens implantation between PRO-149 and Healon® EndoCoat.

3.4 Exploratory objectives

- To compare the intraoperative performance of PRO-149 versus Healon® EndoCoat in cataract phacoemulsification surgery and intraocular lens implantation, as assessed by the surgeon.

3.5 Hypothesis

H_1 : PRO-149 viscoelastic solution is equivalent in safety to Healon® EndoCoat for use as an OVD in phacoemulsification surgery and IOL placement in patients with senile cataracts.

H_0 : PRO-149 viscoelastic solution is not equivalent in safety to Healon® EndoCoat for use as an OVD in phacoemulsification surgery and IOL placement in patients with senile cataract.

4. Study design

4.1 Design Overview

Pilot, controlled, parallel-group, open-label, randomized clinical trial.

4.2 Justification of the study design

The study design (clinical trial) is considered the highest standard of data quality when exploring the effect of an intervention. The development, or pilot, phase for a device corresponds to the study objective, which is to evaluate safety, so the intervention time is short and the required sample size is smaller than that of a pivotal clinical trial. The presence of parallel groups allows for comparisons between the intervention groups on outcome variables. Primary blinding was not considered for this study due to the characteristics of both investigational products; however, the statistical analysis will be blinded.

4.3 Expected duration

The total duration of the study, from the first patient's first visit to the preparation of the final report, is estimated to be 7 months.

The planned recruitment period is 4 months. Considering the proposed sample size of 36 subjects, the average total recruitment rate during the study should be no less than 1 subject enrolled every 4 days.

The approximate duration of each subject in the study is 45 days.

5. Study population

5.1 Eligibility criteria

5.1.1 Inclusion criteria

- Age equal to or greater than 49 years.
- Diagnosis of age-related cataract (senile cataract) requiring cataract phacoemulsification surgery and placement of a monofocal intraocular lens.
Grade I to IV cataracts based on nuclear opacity (opalescence and/or color) of the lens opacity classification system (LOCS III).
- Ability to voluntarily grant informed consent.
- Be able and willing to comply with scheduled visits, treatment plan, and other study procedures.
- Desire and willingness to undergo phacoemulsification surgery and placement of a monofocal IOL.
- Have an anterior chamber depth \geq 2.8 mm as measured by IOL Master.
- Preoperative cardiology evaluation that qualifies the patient for the surgical procedure, with supporting laboratory studies: complete blood count (CBC), three-element blood chemistry (BC), coagulation times (PT/PTT, INR), and electrocardiogram (ECG). If a prior evaluation is available, it must not be performed more than 45 days prior to signing the informed consent form (ICF).

5.1.2 Exclusion criteria

- History of any systemic disease or condition that makes you ineligible for the surgical procedure under sedation and topical anesthesia.
- Diabetes mellitus with A1C \geq 6.5% (48 mmol/mol) or fasting glucose (no caloric intake for \geq 8 hours) of \geq 126 mg/ dL (7.0 mmol/L)
- Uncontrolled systemic hypertension. Defined as blood pressure greater than 140/90 mmHg with the use of three antihypertensives (one of which is a diuretic) at the maximum dose.
- Have a history of eye diseases that could limit the best corrected visual acuity, or be reactivated and/or exacerbated by the surgical procedure or by the use of topical steroids (e.g. retinal detachment, macular degeneration, pathological myopia, proliferative diabetic retinopathy, diabetic macular edema, optic neuritis, uveitis or other types of ocular inflammation, glaucoma, ocular hypertension, corneal dystrophy or ectatic disorder, history of an ocular infection by herpes or varicella zoster).
- Active eye infection.
- Pseudo exfoliation syndrome in the eye to be operated on or other type of zonular involvement.
- Pharmacological mydriasis less than 6 mm.
- Any congenital ocular anomaly in the eye to be operated on.
- Any ocular abnormality that prevents obtaining a reliable Goldmann tonometry in the eye to be operated on.
- An intraocular pressure (IOP) >21 mmHg in the eye to be operated on, or a history of intraocular pressure >21 mmHg with the use of topical steroids.
- A corneal endothelial cell (CEC) density < 1500 cells/mm² in the eye to be operated on.
- History of previous corneal or intraocular surgery.
- Having multiple procedures planned during cataract surgery (i.e., trabeculectomy, relaxing keratotomies, etc.).
- History of ocular trauma in the eye to be operated on (includes surgical procedures).
- Having a one single evaluable eye.
- Having participated in another clinical research study \leq 30 days prior to signing the ICF.
- Having previously participated in this study.

- A history of drug addiction or drug dependence, currently or within the last two years prior to signing the ICF.
- A history of ocular surgical procedures within the last 3 months prior to signing the ICF.
- Any type of surgical intervention scheduled during the study period.
- Be or have an immediate family member (e.g., spouse, parent/legal guardian, sibling, or child) who is a member of the research site or sponsor staff.

5.2 Criteria for elimination and/or substitution of subjects

5.2.1 Elimination criteria

- Withdrawal of informed consent.
- Major deviation from the protocol that could impact the integrity of the results.
- Presentation of an adverse event, whether or not related to the investigational product, which, in the opinion of the PI and/or the sponsor, could affect the subject's ability to safely continue the study procedures.
- Non-tolerability or hypersensitivity to any of the compounds used during the tests (fluorescein, lissamine green, tetracaine).
- Non-tolerability or hypersensitivity to any of the investigational drugs.

5.2.2 Subject substitution

The sponsor, with prior authorization from the research ethics committees, may decide to replace subjects who withdraw their ICF or those who are lost to follow-up, if it is necessary to balance the study groups so that they are evaluable.

5.3 Scrutiny failures

A screening failure is defined as a participant who agrees to participate in the study, giving their consent, but who is not assigned to a treatment group; that is, they do not enter the study. The following information regarding screening failures must be reported, at a minimum:

- Demographic data.
- Details of the counting failure (specify whether due to eligibility criteria, which one, or some other reason for the failure).
- Presence of serious adverse events during the scrutiny.

The above is necessary to comply with the CONSORT guidelines (*Consolidated Standards of Reporting Trials*) for the publication of results or to respond to potential questions from regulatory authorities.

Subjects who do not meet the eligibility criteria for participation in the study due to a specific modifiable factor may be re-screened. Subjects in this situation must use the same initial screening number.

5.4 Recruitment and retention strategies

This is a pilot study and the minimum expected recruitment rate is 1 subject every 4 days.

The duration of the subject's participation in the study is approximately 45 days, during which they will be required to attend six visits in total, which correspond to standard screening and surgery scheduling visits, as well as cataract surgery follow-up visits. Strategies to improve subject retention include, but are not limited to:

- Clearly communicate the importance of the study and the benefits the population will gain from its results.
- Make calls or send text messages to remind yourself of appointments or activities to do.

- Provide a printed calendar and ID card to remind you of upcoming appointments and activities, as well as their estimated duration.
- Offer flexible business hours.
- Systematic organization of the study procedures, so that the subject does not stay longer than necessary during his visit.
- Minimize subject wait times.

All materials to be delivered to the subject or recruitment strategies implemented by the Centers will be submitted for approval by the corresponding committees.

5.5 Procedure in case of early discontinuation

For this protocol, early discontinuation is defined as those subjects who were randomized, and who at some point were active subjects in the study, but their final evaluation could not be completed.

If the subject does not complete their participation due to withdrawal of consent or a major deviation, the last visit at which their withdrawal was determined will be considered their final visit. Subjects withdrawn due to the presence of AEs will continue the follow-up as determined until their AE is resolved.

In cases where the participating subject does not attend their appointment, the research site will call to determine the reason and will attempt to schedule a new appointment within the established window or an unscheduled appointment. If an appointment cannot be scheduled, the subject will be considered lost to follow-up, and the presence of adverse events and the reason for discontinuing the study will be asked as minimum data.

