1.2 Study diagram

ScrV: Scrutiny visit; **SchV:** Scheduling visit; **SurV:** Surgery visit; **1SV:** 1st safety visit; **2SV:** 2nd safety visit; **FV:** Final visit.
ScrV: includes specular microscopy, IOL calculation and corneal pachymetry.
FV: includes specular microscopy and corneal pachymetry.

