7.4 Outcome variables

7.4.1 Primary outcome variables

- Changes in CEC density.
- IOP.

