7.4.4.1 Corneal endothelial cell density

Specular microscopy allows a clear view of live endothelial cells without altering their function or morphology. In turn, a surface area count can be performed to determine if there is an alteration in the shape or size of the endothelial cells, parameters that must be taken into account to determine the functional capacity of the corneal endothelium. CEC density decreases over time, due to diseases and intraocular surgical procedures. Analysis of CEC density will be performed using a specular microscope

(the make and model of the equipment must be specified). The density in cells/mm² will be recorded in the eCRF. The area and strategy used in the scrutiny visit must be the same as the final visit.

Management as AE: This value, by itself, will not be considered an AE regardless of the changes; the AE will correspond in each case to a clinical corneal decompensation when so judged by the PI.

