10.1.3 Procedure for handling missing data

The safety assessment will include in the analysis all subjects who have been exposed to any of the interventions, regardless of the visit at which they were eliminated from the study (ITT; intention-to-treat population).

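### CEC density has one post-operative reading, at Day 29, and no rule secures it in treated subjects who leave the study early

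*Combined protocol and SAP*

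**What the plan says.** Section 7.4.1 lists "Changes in CEC density" as a primary outcome, alongside IOP. The study diagram (1.2) notes that the final visit "includes specular microscopy and corneal pachymetry". The schedule (1.3) and Table 3 place specular microscopy at screening and at the final visit (Day 29 ±2) only. Section 7.4.4.1 assumes the same two time points: "The area and strategy used in the scrutiny visit must be the same as the final visit".

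Section 5.2.1 allows elimination after surgery. The grounds include a major deviation and "Presentation of an adverse event, whether or not related to the investigational product", where the investigator or sponsor judges that it "could affect the subject's ability to safely continue the study procedures". Section 5.5 then sets three rules:

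- **Consent withdrawal or major deviation:** "the last visit at which their withdrawal was determined will be considered their final visit".
- **Adverse-event withdrawal:** follow-up goes on until the event resolves. No end-of-study procedures are named.
- **Missed appointment:** the site calls and tries to rebook, in the window or as an unscheduled visit. "If an appointment cannot be scheduled, the subject will be considered lost to follow-up". The minimum data are then adverse events and the reason for stopping.

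Section 10.1.3 keeps every exposed subject in the safety assessment, "regardless of the visit at which they were eliminated from the study". Section 10.1.5 bases the analysis for the study objective on subjects who complete all visits.

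**The concern.** Treatment duration in the synopsis is the operation itself. Eliminating a subject afterwards cannot reduce exposure to the device; it can only cost data. The continuity assessment, where the investigator checks for reasons to withdraw a subject, is scheduled at the scheduling, surgery, Day 1 and Day 8 visits. So every scheduled post-operative decision to eliminate falls before the one post-operative CEC reading.

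The plan intends to count these subjects as exposed, but gives no means of obtaining their CEC value and no method for handling its absence. Section 7.4.4.3 lists corneal decompensation, ocular inflammation and raised IOP among the events that may occur with either product. An eye that leaves because of such an event could plausibly have lost more endothelium than one that stays. Section 10.1.2 calls the product safe when no clinical and statistical difference is found in the primary outcomes, so losing the worst eyes from one arm would help it pass. Replacing subjects under 5.2.2 restores the count but not the missing eye.

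**Working it through.** **1. Is there any other post-operative CEC reading?** The study diagram, the schedule, Table 3 and sections 7.5.1.4 to 7.5.1.6 agree that there is not. Pachymetry has the same single point. IOP differs: it is also measured at Day 1 and Day 8.

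**2. Does any exit route secure a Day 29 CEC value?**

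- *Major deviation.* The withdrawal visit becomes the final visit. Section 5.5 does not say whether the final-visit procedures are then done. If not, there is no post-operative value. If so, the reading may come from Day 1 or Day 8 and is not a Day 29 value.
- *Adverse event.* Follow-up is tied to resolution. An event resolving on Day 12, say, satisfies the rule with no specular microscopy done. A Day 29 reading is neither required nor forbidden.
- *Lost to follow-up.* The rule applies to any appointment. A Day 1 or Day 8 visit that cannot be rebooked triggers it while Day 29 is still ahead.
- *Unscheduled visits (7.5.2).* These call for adverse-event data. Specular microscopy is not mentioned.

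No route secures the value.

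**3. The plan's own loss figure.** Section 10.2.2 raises 14 per arm to 18 for 20% losses: 14 / (1 − 0.20) = 17.5, rounded up to 18. That step reproduces. The 14 does not: the stated formula with p = p₀ = 0.0697 (equality is my assumption, since only one rate is given) and a 5% margin gives about 222. That is a separate matter, and nothing here rests on it. The gap of 18 − 14 = 4 per arm is an allowance, not a forecast of damaged eyes; section 10.1.4 defines the losses as loss to follow-up or consent withdrawal.

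**4. Illustration in one arm.** Inputs:

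- 18 eyes per arm (10.2.1).
- 7% mean loss in completers, rounded from the 6.97% in 10.2.2.
- L, the mean loss in unmeasured eyes. This is an assumption; the documents give no figure.

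With k eyes unmeasured, the completer mean understates that arm's mean loss by

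shift = [(18 − k)·7 + k·L] / 18 − 7 = k(L − 7) / 18.

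| k | L = 10% | L = 20% | L = 30% |
|---|---|---|---|
| 1 | 3/18 = 0.2 | 13/18 = 0.7 | 23/18 = 1.3 |
| 3 | 9/18 = 0.5 | 39/18 = 2.2 | 69/18 = 3.8 |

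Values are percentage points. If unmeasured eyes lose the same 7% as completers, the shift is zero.

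**5. From one arm to the comparison.** The bias in the difference is the PRO-149 shift minus the comparator shift. Similar missingness in both arms largely cancels. A genuinely worse PRO-149 would be hidden only if its missing eyes were more numerous or more damaged than the comparator's.

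**The case against.** A reader might infer that the rules end follow-up for everyone who does badly. Section 5.5 says otherwise: adverse-event withdrawals continue to be followed. What is missing is a CEC requirement within that follow-up. The sentence about the final visit covers only consent withdrawal and major deviation.

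A reader might infer that one missed visit removes a subject. It does so only when rebooking fails.

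A reader might also infer that Day 1 or Day 8 readings would be mixed with Day 29 readings. No passage pools them, and the completer set in 10.1.5 would exclude them.

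Elimination for an adverse event is also narrower than it first looks. It needs a judgement about safe continuation. IOP of 30 mmHg or more and cell or flare grades of 3 or more are reportable events, not automatic grounds for removal. In the 400-patient study described in 2.2.2, only three adverse events were not raised IOP, and none was corneal decompensation; 3/400 × 36 is about 0.3 such events in a trial of this size. This tells against large numbers, although that study did not include PRO-149, which has no earlier clinical data (2.3.1).

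Finally, it is tempting to express the shift as a share of the 5% margin. That margin appears only in the sample-size section and the decision rule in 10.1.2 does not use it, so the ratio would measure nothing that the plan tests.

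All of these points limit the claim. None supplies a rule that secures the Day 29 value.

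**Conclusion.** The concern holds as a gap in data collection. CEC density has a single post-operative reading, and exposed subjects who leave after surgery have no assured value at that point, although 10.1.3 counts them in the safety analysis. That part follows from the text alone.

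The size is not established. The shifts of 0.7–1.3 points (one eye of 18) and 2.2–3.8 points (three of 18) describe one arm and rest on an assumed 20–30% loss in every unmeasured eye. Bias towards no difference further requires more, or worse, missing eyes on PRO-149. The documents show neither that this will happen nor that it cannot. The case for change is that the omission is cheap to prevent and cannot be repaired at analysis.

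**What to change.** In sections 5.2.1 and 5.5:

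- State that every subject in whom the OVD was applied, and who has not withdrawn consent, is asked to attend the Day 29 ±2 visit for the already planned specular microscopy, pachymetry, tonometry and BCVA. This applies even after elimination for an adverse event or deviation, or after a missed earlier visit.
- Remove the rule that turns an earlier visit into the final visit after a deviation.
- Class a subject as lost to follow-up only when the Day 29 window has closed without attendance.
- Record any early exit reading under its actual day, never as Day 29.

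In section 10.1.3, state that the collected values enter the all-exposed analysis of CEC density. Without this the gain is partial, because the completer set in 10.1.5 would still leave out anyone who was eliminated early or missed a visit outright.

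The cost is a wording amendment and one already planned visit for a few subjects. No new procedure or equipment is needed.
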